**Engaging Black Youth in Depression and Suicide Prevention Treatment Within Urban Schools**

**1 R34 MH119290-01**

**06/28/2021**

**NCT03940508**

## Statistical Design and Power

With a sample size of only 30 per condition (total  $N = 60$ ), power is a challenge. For a traditional single degree of freedom contrast of means, assuming an alpha level of 0.05 for a two tailed test and power of 0.80, the effect size sensitivity corresponds to a population Cohen's  $d$  of 0.75, which represents about 12% explained variance. This represents sensitivity to a large effect. For a correlation coefficient,  $N = 60$  and using the same general power parameters as above, the effect size sensitivity corresponds to a population correlation of 0.35, or, again, about 12% explained variance.

Approaches to increasing statistical power generally focus on increasing sample size, but an alternative strategy is to introduce covariates that reduce within-condition error. This approach leads to a more sensitive significance test for the treatment effect. In the proposed R34, we will increase the statistical power by adjusting for relevant covariates measured at baseline. Covariate adjustment for a pretreatment score on each outcome measure will substantially increase statistical power. For example, if pretreatment and post treatment scores correlate  $r=.65$  (which seems reasonable based on our prior research, then the effect size sensitivity for an  $N$  of 30 per group and power of 0.80 corresponds to a Cohen's  $d$  of about 0.55. Importantly, as we explore power and as a function of baseline and other covariates, we can make more informed sample size decisions for the larger R01. In general, the robust methods of analysis will be as powerful or more powerful than the least squares methods, so the power estimates above apply, conservatively, to the robust methods as well.

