1 R34 MH119290-01

Version date 4/17/2019

Summary of the Research

The overall goal of this study is to examine the effectiveness of the Making Connections Intervention, hereafter referred to as the MCI. Based on the Unified Theory of Behavior and Stages of Change Theory, the MCI is designed to facilitate adolescents' identification of perceptual and actual barriers that influence their mental health treatment acceptability (i.e. engagement, perceived relevance, and satisfaction), and equip them with the skills to overcome these barriers at the initiation and/or during the course of treatment. As a test of the MCI, our target population was urban, Black adolescents screened for depression and referred for Interpersonal Psychotherapy for Depressed Adolescents, or IPT-A, for treatment. Prior research by the PI indicates that depressed, Black adolescents are likely to have untreated depression due to negative family influences, negative perceptions of services and providers, or self-stigma associated with experiencing depressive symptoms. This is of public health significance because: (1) this group uses less mental health services than any other adolescent group, and non-financial factors (e.g. mental illness stigma, negative perception of providers/services) plays a significant role in their lower service use; (2) if/when they do enter treatment, low engagement and early termination typify their experiences; and (3) suicide, a byproduct of untreated depression, has increased among this group, narrowing the gap in suicide rates between White and Black adolescents. To date, limited work has been done to improve treatment acceptability among urban, Black adolescents with depression, especially those in their middle-school age years. This study proposes a small-scale trial in New York City DOE school-based mental health clinics throughout the Bronx, where Black youth would be randomized to receive the MCI+IPT-A or IPT-A alone.

Project Information II

Description of study procedures:

- a. The study will be conducted at six (6) New York City Department of Education (DOE) Middle and High School School-Based Mental Health Clinics.

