- b. Participants will need to sign consent (caregivers) and assent (youth) forms. Following enrollment, youth and caregivers will be given a baseline assessment consisting of a series of questionnaires. Both youth and caregivers assigned to the MCI + IPT-A group will attend one or two MCI sessions lasting approximately 45 minutes. The youth participants will continue to receive IPT-A for 12 sessions and will be given additional assessment questionnaires at weeks 4, 8, and 12. Youth in the IPT-A only group will begin IPT-A sessions immediately following enrollment and will follow the same assessment schedule. Assessments, screenings, and MCI and IPT-A sessions will be conducted at the youth's school.
- c. The MCI coupled with the IPT-A will consist of 13-15 intervention sessions. The IPT-A alone will consist of 12-15 intervention sessions. The MCI will occur with parents or legal guardians and students for one hour (60-75 minutes) over 1-2 sessions (Note: the screening and initial assessment will occur prior to the MCI session). The remaining 12-15 sessions will focus on the delivery of the evidence-based depression treatment, IPT-A, which will occur in weekly 30-45 minute individual therapy sessions (over 12 weeks, additional if a week is skipped) with the students and allowing possible concurrent sessions with the parent or legal guardian as needed. Thus, the intervention should last for approximately 3-4 months.

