permission to be contacted form, along with a letter describing our study. If caregivers agree to be contacted, the SMH staff will share with the research staff the contact information of students who scoring above the clinical cutoff of 11 (range 0 to 27). Astor Services for Children & Families used the school-wide screening method with the Strengths and Difficulties Questionnaire in 2015 and had an approximately 50% return rate on the screenings/consent forms. Research staff will not receive names of students whose parents do not provide a permission to be contacted form. Of the received forms, the research staff will contact the family to set up a time to consent/assent for the study and screen the adolescent using our standard screening procedure, which is to administer the Center for Epidemiologic Studies Depression Scale (CES-D). Second way we also will recruit participants is that using another standard of care in SMH service delivery, which is to recruit through the school-based clinics among those students presenting to services for mental health needs. That is, SMH staff at the participating schools currently receive referrals from NYC DOE social workers, guidance counselors, administrators, teachers, other school-based providers, family members, and self-referrals. All referrals are screened using the PHQ-9. Upon receipt of referrals, the SMH staff person will share a brochure of the study and a letter to be shared with the family, along with a permission to be contacted form. Following assessment, [name] and [name] will review assessment, establish eligibility, and follow random assignment procedures. Randomization lists will be prepared by [name] who will have no contact with participants, clinicians, or study staff members. We will randomize within schools and provide clinicians information per each case about whether the participant will receive the MCI + IPT-A or IPT-A only. Clinicians will complete fidelity assessments, and we will randomly listen to audiotapes of sessions to document the extent of contamination or the potential of it. We will also make sure to discuss instances of contamination (or the potential of it) during weekly supervision with the clinicians. Note: We will keep track of the % of families who return the permission to be contacted forms. Research staff will follow-up on all returned forms and schedule a time to consent/assent for the study and screen the adolescent using our standard screening procedure

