depressive symptoms. For example, as a standard of practice in the IPT-A treatment, SMH clinicians assess current symptom levels at the beginning of each session. Further, SMH clinicians complete the Children's Global Assessment Scale (C-GAS) to assess for global impairment associated with mood disorder. Additionally, the Hamilton Rating Scale for Depression (HRSD) and Center for Epidemiological Studies-Depression Scale (CES-D) are administered at baseline, post-MCI session, and at weeks 4, 8 and 12. If at any time the symptoms, as indicated by the HRSD and CES-D, reach a clinically severe level (HRSD score of 28 or greater; CES-D score of 31 or greater), the PI and SMH clinicians immediately ask follow-up questions to determine whether the youth is expressing suicidal ideation; if suicidal ideation was indicated, the PI and SMH clinicians further assess whether the youth has a plan, whether there is access and means to follow through with a plan, the level of suicidal intent and the presence of current suicidal gestures. We also contact the caregiver and provided information about emergency psychiatric services for determination of whether hospitalization is necessary. If there was a pattern of worsening depressive symptoms or de-compensation in the absence of suicidal intent during the course of the study (as measured by the Clinical Global Impressions (CGI), which was given weekly by the SMH clinician and indicated by a 6 or 7 on the CGI for 2 consecutive weeks), the PI in consultation with the SMH clinicians will make a determination of whether the youth is: (1) appropriate for the study; or (2) in need of more emergent psychiatric care such as hospitalization. Referral may also be made back to a primary care physician or to community-based mental health services in instances where participants might worsen during the course of the study. Again, guidance on this determination is informed on a session-by-session basis (e.g. symptom query is a standard practice of the IPT-A treatment) and via the standardized assessments of depression (e.g. HRSD and CES-D). If hospitalization was necessary, information on psychiatric services (e.g. hospitalization) will be provided to the caregiver.

Benefits of the Study

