Participants experience minimal risks and receive high quality mental health services from master's level SMH clinicians in an effort to help reduce presenting issues. Participants may gain knowledge of the therapy process and learn problem solving skills to reduce hesitancy to engage in treatment. Participants may experience a reduction in depression as an outcome of completing the full depression intervention.

However, participants may not receive any direct benefit from participating in the study.

Results of this study will inform the preparation of a future federal grant application proposal (e.g. NIH R01) to address the effectiveness of the intervention approach outlined here in a larger scale trial. In particular, a future randomized controlled trial will be conducted to further test or refine the MCI intervention for SMH/community-based services. An intervention that will help reduce barriers to care and improve engagement in therapy would benefit the community greatly, particularly for those groups who experience many challenges in obtaining mental health services such as Black adolescents in an urban setting.

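### Does the SAP promise a baseline-adjustment power gain for outcomes that cannot have a baseline score?

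*SAP*

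**What the plan says.** The SAP (Statistical Design and Power) gives two sensitivity figures for 30 per arm, two-sided alpha 0.05 and 80% power. The first, without covariates, is d = 0.75. The second is about 0.55 and assumes that pre- and post-treatment scores correlate at .65. Two sentences link them. The broader one says "we will increase the statistical power by adjusting for relevant covariates measured at baseline". The narrower one says "Covariate adjustment for a pretreatment score on each outcome measure will substantially increase statistical power", with no exception for any outcome.

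The protocol's Summary of the Research describes the MCI as addressing barriers to "mental health treatment acceptability (i.e. engagement, perceived relevance, and satisfaction". Its section Benefits of the Study speaks of an intervention that would "reduce barriers to care and improve engagement in therapy".

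On timing, Description of study procedures has a "baseline assessment consisting of a series of questionnaires" after enrollment and notes that "the screening and initial assessment will occur prior to the MCI session". Under Participant Identification, Recruitment, & Selection, named staff "will review assessment, establish eligibility, and follow random assignment procedures" once the assessment is done. Under Risks of the Study, the HRSD and CES-D "are administered at baseline, post-MCI session, and at weeks 4, 8 and 12".

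Neither document lists the outcomes, names an instrument for engagement or satisfaction, or itemises the baseline questionnaires.

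**The concern.** Adjusting for an outcome's own baseline score helps only if that score exists. A youth who has not started IPT-A cannot report engagement in it or satisfaction with it, and baseline comes before both the MCI and IPT-A. If such measures are outcomes, the word *each* claims too much for the construct the MCI is meant to change. A reader might then take 0.55 as the trial's sensitivity for acceptability when 0.75 is the figure that applies. That could matter for the later R01, because the SAP says its power work will inform that trial's sample size.

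**Working it through.** **Inputs.** All are from the SAP: n = 30 per arm, two-sided alpha 0.05, power 0.80, r = .65, and detectable d of 0.75 (unadjusted) and about 0.55 (adjusted). I assume all 30 per arm are analysed and the outcome is a difference in means with SD 1.

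**Step 1: reproduce the unadjusted figure.** Detectable d = (z₀.₉₇₅ + z₀.₈₀) × √(2/n) = (1.960 + 0.842) × √(2/30) = 2.802 × 0.2582 = 0.723. The noncentral t with 58 df gives 0.736. At the SAP's d = 0.75, power is 82.8% (normal) or 81.5% (t). The SAP's figure is right and slightly cautious.

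**Step 2: reproduce the adjusted figure.** Multiply by √(1 − r²) = √(1 − 0.4225) = 0.760. This gives 0.723 × 0.760 = 0.550 (normal), or 0.559 by t with 57 df. Power at d = 0.55 is 80.0% or 78.7%. A change-score analysis would give 0.736 × √(2 × 0.35) = 0.615, so the SAP's figure is the covariate-adjusted one.

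**Step 3: an outcome with no baseline score.** With r = 0 the detectable d stays at 0.72 (normal) or 0.74 (t). Power at d = 0.55 is 57% or 55%. Reaching 80% there would take 52 or 53 per arm.

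**Step 4: a substitute baseline covariate.** The documents give no correlation for one, so this range is assumed (t-based):

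| Assumed R | Detectable d | Power at d = 0.55 |
|---|---|---|
| .1 | 0.73 | 55.8% |
| .3 | 0.70 | 59.3% |
| .5 | 0.64 | 67.7% |

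Reaching 0.55 would need R = √(1 − (0.55/0.736)²), about 0.66.

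**Step 5: is there such an outcome in the documents?**

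- HRSD and CES-D have baseline scores (Risks of the Study), and so does C-GAS (Inclusion Criteria). For these the narrower SAP sentence holds.
- The CGI is mentioned only as a weekly safety trigger, not as an outcome.
- Engagement, perceived relevance and satisfaction appear as the construct the MCI addresses. No endpoint, scale or schedule is given for them. The Summary of the Research links low service use to perceptions of services and providers and to self-stigma. Attitudes of that kind can be asked about before therapy.

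So Step 3 applies only if two unstated things are both true: engagement or satisfaction is an analysed outcome, and it is measured with respect to the study treatment.

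**The case for a change.** The best case for a change is that acceptability is no side issue. Both arms receive IPT-A, so the randomised contrast isolates the MCI, and the MCI's stated target is acceptability. Exclusion criterion 5 bars youth already in active depression treatment other than medication. At baseline there is therefore no study therapy, and no other current non-drug depression treatment, to engage with or be satisfied with. The *if* in the SAP's example covers the size of the correlation, not whether a baseline score exists. Pointing to other covariates does not rescue 0.55, since none is shown to reach R of about 0.66. Rewording would also cost almost nothing.

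Much of this stands. The word *each* is unqualified, IPT-specific engagement cannot be scored before IPT-A, and 0.55 would not carry over to such a measure. But the exclusion criterion does not prevent scoring views of mental health services in general, and the argument still needs an outcome that the documents do not name. If engagement were recorded as attendance or retention, neither 0.75 nor 0.55 would be the natural figure. A clarifying phrase would do no harm, but it would correct no figure and alter no analysis.

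**Conclusion.** No change to the plan is needed. Both printed figures are correct for what they describe: about 0.75 without a covariate and about 0.55 with an outcome's own baseline score at r = .65. The most that could be at stake is the gap between them, with power at d = 0.55 of about 55% instead of about 80%. That would apply only to an outcome first measurable after treatment starts, and the documents identify none.

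The SAP contains its own limits. It opens by calling power a challenge, prints 0.75 first, presents 0.55 as an example, and never assigns 0.55 to acceptability. Its broader sentence on baseline covariates tells analysts what to do where an outcome has no pretreatment score. They would adjust for the score where it exists and for other baseline measures otherwise.

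The sample size is fixed at 60, and the SAP intends to explore power by covariate before sizing the R01. What can be shown is only that outcomes and their first measurement times are not listed, which is missing detail and not an error in the power statement. This conclusion assumes 30 analysed per arm and outcomes compared as means. It would need another look if an outcome list showed a main acceptability measure with no baseline score and 0.55 quoted as its sensitivity.
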